9.5.1.5.2 SERIOUS ADVERSE EVENTS AND EVENTS ASSOCIATED WITH SPECIAL SITUATIONS

A SAE is any untoward medical occurrence that at any dose:

- Results in death
- Is life-threatening (ie, the subject was at immediate risk of death from the AE as it occurred; this does not include an event that, had it occurred in a more severe form or was allowed to continue, might have caused death)
- Requires inpatient hospitalization or prolongation of existing hospitalization
- Results in persistent or significant disability/incapacity
- Is a congenital anomaly/birth defect (in the child of a subject who was exposed to the study drug)

Other important medical events that may not be immediately life-threatening or result in death or hospitalization but, when based on appropriate medical judgment, may jeopardize the subject or may require intervention to prevent one of the outcomes in the definition of SAE listed above should also be considered SAEs. Medical and scientific judgment should be exercised in deciding whether expedited reporting is appropriate in such situations.

In addition to the above, events associated with special situations include pregnancy or exposure to study drug through breastfeeding; AEs associated with study drug overdose, misuse, abuse, or medication error. These events associated with special situations are to be captured using the SAE procedures but are to be considered as SAEs only if they meet one of the above criteria. All AEs associated with special situations are to be reported on the CRF whether or not they meet the criteria for SAEs.

All SAEs must be followed to resolution or, if resolution is unlikely, to stabilization.

The following hospitalizations are not considered to be SAEs because there is no “AE” (ie, there is no untoward medical occurrence) associated with the hospitalization:

- Hospitalizations for respite care
- Planned hospitalizations required by the protocol
- Hospitalization planned before informed consent (where the condition requiring the hospitalization has not changed after study drug administration)
- Hospitalization for administration of study drug or insertion of access for administration of study drug
- Hospitalization for routine maintenance of a device (eg, battery replacement) that was in place before study entry

If possible, a blood sample for the measurement of study drug plasma concentration should be drawn at the 1st report of an SAE or a severe unexpected AE and at its resolution.

9.5.1.5.3 LABORATORY MEASUREMENTS

Clinical laboratory tests to be performed, including hematology, chemistry, and urinalysis, are summarized in [Table 3](#). Subjects should be in a seated or supine position during blood collection. The Schedule of Procedures/Assessments ([Table 4](#)) shows the visits and time points at which blood for clinical laboratory tests and urine for urinalysis will be collected in the study (Core Study).

Table 3 Clinical Laboratory Tests

Category	Parameters
Hematology	Hematocrit, hemoglobin, platelets, RBC count, and WBC count with differential (basophils, eosinophils, lymphocytes, monocytes, neutrophils) (revised per Amendment 01)
Chemistry	
Electrolytes	Chloride, potassium, sodium
Liver function tests	Alanine aminotransferase, alkaline phosphatase, aspartate aminotransferase, gamma glutamyl transpeptidase, direct bilirubin, total bilirubin
Renal function tests	Blood urea/blood urea nitrogen, creatinine
Other	Albumin, calcium, cholesterol, globulin, glucose ^a , lactate dehydrogenase, phosphorus, total protein, triglycerides ^a , uric acid
Urinalysis	Bacteria, casts, crystals, epithelial cells, glucose, ketones, occult blood, pH, protein, RBCs, specific gravity, WBCs, Urine drug screen ^b (revised per Amendment 01)

RBC = red blood cell, WBC = white blood cell.

- a: Fasting samples to be taken at baseline and at end of treatment or early discontinuation, with fasting window (interval) between 2 and 4 hours.
- b: To be performed only at baseline. (revised per Amendment 01)

Clinical laboratory tests during the Core Study and Extension A will be performed by a central laboratory. (revised per Amendment 03) All blood and urine samples will be collected and sent to the central laboratory on the day of collection unless otherwise instructed. In cases of a safety concern, blood samples will be split (or 2 samples drawn) to allow a local laboratory analysis in addition to the central laboratory.

A laboratory abnormality may meet the criteria to qualify as an AE as described in this protocol (see [Section 9.5.1.5.1](#) and the CRF Completion Guidelines). In these instances, the AE corresponding to the laboratory abnormality will be recorded on the AE CRF.

9.5.1.5.4 VITAL SIGNS AND WEIGHT MEASUREMENTS

Vital sign measurements (ie, systolic and diastolic blood pressure [BP] [mmHg], pulse [beats per minute], respiratory rate [per minute], body temperature [in centigrade]), and weight (kg) will be obtained at the visits designated in the Schedule of Procedures/Assessments ([Table 4](#)) by a validated method. BP and pulse will be measured after the subject has been supine for 5 minutes. All BP measurements should be performed on the same arm, preferably by the same person.

9.5.1.5.5 PHYSICAL EXAMINATIONS

Physical examinations will be performed as designated in the Schedule of Procedures/Assessments ([Table 4](#)). Documentation of the physical examination will be

included in the source documentation at the site. Only changes from screening physical examination findings that meet the definition of an AE will be recorded on the AEs CRF.

9.5.1.5.6 ELECTROCARDIOGRAMS

ECGs will be obtained as designated in the Schedule of Procedures/Assessments (Table 4).

An ECG abnormality may meet the criteria of an AE as described in this protocol (see Section 9.5.1.5.1) and the CRF Completion Guidelines. In these instances, the AE corresponding to the ECG abnormality will be recorded on the AEs CRF.

9.5.1.5.7 OTHER SAFETY ASSESSMENTS

C-SSRS

An assessment of suicidality using the C-SSRS will be performed for subjects aged 6 years and older at the time of consent/assent at Screening/Baseline, Day 1 postdosing, every visit, including after the last dose of study drug, and at the Termination Visit, as designated in the Schedule of Procedures/Assessments (Table 4).

Pregnancy Test

A serum β -hCG test will be performed for female subjects age 8 years old and above, or of child-bearing potential, only. A sample of blood will be taken at screening; at all other time points a urine pregnancy test will be performed as specified in the Schedule of Procedures/Assessments (Table 4). If urine can not be obtained for pregnancy testing after screening, a serum pregnancy test will be performed. (revised per Amendment 01)

EEG

An EEG will be performed over a minimum of 1-hour and up to a 2-hour period in awake and sleeping states at the visits designated in Table 4.

ABNAS

The ABNAS assessment measures 5 aspects of cognitive function: fatigue, memory, concentration, motor speed, and reading, using a 4-point scale. The assessment is a measure of patient-perceived cognitive effects of AEDs.

This instrument aimed at assessing patient perceived drug-related cognitive impairment. It will be assessed at designated time points as specified in the Schedule of Procedures/Assessments (Table 4).

CBCL

The CBCL is a questionnaire to assess behavioral and emotional problems in children as reported by the primary caregiver. It is standardized to evaluate maladaptive behavioral and

emotional problems in ages 2 to 18 years. It will be assessed at designated time points as specified in the Schedule of Procedures/Assessments ([Table 4](#)).

LGPT

The LGPT is a manipulative dexterity test requiring complex visual-motor coordination and will be assessed at designated time points as specified in the Schedule of Procedures/Assessments ([Table 4](#)).

9.5.1.6 Other Assessments

EQ-5D-Y

A health related quality of life questionnaire (EQ-5D-Y) will be administered. For patients with mental disabilities and patients ages 4 to 7, caregivers, or parents will complete the proxy EQ-5D-Y. For ages 8 to 11 with no mental disabilities, patients will self-complete the EQ-5D-Y. Patients ages 8 to 11 with physical disabilities but no mental disabilities may have the EQ-5D-Y read to them and their responses recorded by a caregiver, parent, or study coordinator. EQ-5D-Y will be administered at the visits designated in [Table 4](#).

CGI

The CGI, Clinical Global Impression of Severity (CGIS), and CGIC will be administered at the visits designated in [Table 4](#). Telephone interviews with the subjects and/or caregiver will be conducted to ensure that subjects are completing their seizure diaries regularly and to assess AEs, study drug compliance, and concomitant medications, including AEDs.

Details for all assessments in the Extension A and Extension B can be found in [Appendix 1](#) and [Appendix 2](#), respectively. (revised per Amendment 03)

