The EuroQol 5 Dimensions-Youth (EQ-5D-Y) questionnaire will be administered to assess how perampanel impacts patients' health-related quality of life (HRQL). HRQL assessment is a requirement for reimbursement submissions both as a qualitative assessment of the net impact of a drug's clinical benefit and AE profile on patients as well as to quantitatively adjust incremental life-year estimates in economic models by the quality of those life-years gained. The EQ-5D is a well-accepted instrument for assessing HRQL for these purposes. The EQ-5D-Y been developed by EuroQol to assess HRQL in children ages 15 and younger. The same five concepts of mobility, self-care, ability to participate in usual activities, pain, and anxiety/depression are assessed; only the language utilized to elicit this information has been modified to be child-appropriate (eg, simpler vocabulary and child-appropriate examples of usual activities). A proxy version of the EQ-5D-Y is available for children aged 4 to 7 so that caregivers may complete the questionnaire for children whose literacy level may be insufficient.

During the Core Study, no change of concomitant AEDs is allowed. However, during the Extension Maintenance Period, addition, deletion, and dose changes to the concomitant AEDs are allowed. Conversion to monotherapy on perampanel is also permitted at the discretion of the investigator, if it is considered appropriate to control the seizures.

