9.3.1 Inclusion Criteria

Subjects must meet all of the following criteria to be included in this study:

1. Have a diagnosis of epilepsy with POS with or without secondarily generalized seizures or PGTC according to the ILAE Classification of Epileptic Seizures (1981). Diagnosis should have been established at least 6 months prior to Visit 1 by clinical history and an EEG that is consistent with the diagnosis; normal interictal EEGs will be allowed provided that the subject meets the other diagnosis criterion (ie, clinical history).
2. Male or female subject, from age 4 to less than 12 years at the time of informed consent/assent.
3. Have a minimum weight of 16 kg (35 lb).
4. Have had a brain imaging (eg, magnetic resonance imaging [MRI] scan or computed tomography [CT]) before Visit 1 that ruled out a progressive cause of epilepsy.
5. During the 12 weeks \pm 3 days (4 weeks \pm 3 days in Japan only) prior to Visit 2, subjects must have had equal or greater than 1 POS or 1 PGTC seizure. (revised per Amendments 01 and 02) Only simple POS with motor signs, complex POS, and complex POS with secondary generalization are counted toward this inclusion for POS.
6. Are currently being treated with stable doses of 1 to a maximum of 3 approved AEDs. (revised per Amendment 01) Doses must be stable for at least 4 weeks before to Visit 1; in the case where a new AED regimen has been initiated for a subject, the dose must be stable for at least 8 weeks prior to Visit 1. Only 1 EIAED (defined as carbamazepine, phenytoin, oxcarbazepine, or eslicarbazepine) out of the maximum of 3 AEDs is allowed (A vagal nerve stimulator [VNS] will be counted as one of the 3 allowed AEDs). (revised per Amendment 01)

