9.7.1.1.3 EXPLORATORY ENDPOINT

Change from baseline at Week 23 and Week 52 in EQ-5D-Y.

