#### 5.4.3 Other Efficacy Analyses

The score of EQ-5D-Y each items (Mobility, Looking after myself, Doing usual activities, Having pain or discomfort, Feeling worried, sad or unhappy) will be summarized for each visit using frequency count (number and percentage). The measurement and the change from baseline of EQ-5D-Y VAS at each visit will be summarized using descriptive statistics (n, mean, standard deviation, median, minimum and maximum).

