## 5.7 Exploratory Analyses

The change from baseline in EQ-5D-Y will be summarized by age and disease cohorts, and by the presence or absence of concomitant EIAED, using descriptive statistics.

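### The EQ-5D-Y respondent is set by age band with no age reference date, so a child who turns 8 on study can have a proxy baseline subtracted from a self-rated follow-up.

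*Protocol*

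**What the plan says.** Protocol 9.5.1.6, repeated in the synopsis, gives two rules for who answers. The first is: "For patients with mental disabilities and patients ages 4 to 7, caregivers, or parents will complete the proxy EQ-5D-Y". The second is: "For ages 8 to 11 with no mental disabilities, patients will self-complete the EQ-5D-Y". Section 7.2 describes the instrument in the same way ("A proxy version of the EQ-5D-Y is available for children aged 4 to 7 so that caregivers may complete the questionnaire"). None of these places says at what date age is read, or that the respondent used at baseline is kept.

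Entry is open to any "Male or female subject, from age 4 to less than 12 years at the time of informed consent/assent", so 7-year-olds enrol and can turn 8 on study. Under Protocol Tables 4 and 5 the scale is given at Week 0, Week 23 and Week 52, and at early discontinuation. The exploratory endpoint in 9.7.1.1.3 is: "Change from baseline at Week 23 and Week 52 in EQ-5D-Y".

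Section 5.4.3 of both SAPs tabulates the five items by visit and adds a change score for the VAS: "The measurement and the change from baseline of EQ-5D-Y VAS at each visit will be summarized". Extension SAP 5.7 goes further: "The change from baseline in EQ-5D-Y will be summarized by age and disease cohorts". The age cohorts are 4 to <7 and 7 to <12. The only EQ-5D-Y data-handling rule, in 8.1.3 of both SAPs, concerns which visit is used. Neither SAP mentions respondent type.

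**The concern.** A change from baseline means what it says only if the same kind of rater gives both values. If a parent rates the child at Week 0 and the child rates himself or herself later, the difference contains any parent-child disagreement as well as any change in health. The study has a single arm, so there is no control group in which a rater effect could cancel; it would appear as change on perampanel.

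The age-8 boundary falls inside the 7 to <12 cohort. That cohort therefore mixes children who are proxy-rated throughout, children who self-rate throughout, and possibly children who move from one to the other. Tabulating by age cohort does not separate them.

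What is at stake is the trial's one exploratory endpoint and the health-utility objective it serves. Protocol 7.2 says that such data feed reimbursement submissions and economic models.

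**Working it through.** **Step 1: the text.** The plan states no figure on this point, so there is none to reproduce. Setting the age-dependent instruments side by side shows what EQ-5D-Y lacks:

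| Instrument | Age rule | Age reference date | Kept separate in the SAPs |
|---|---|---|---|
| C-SSRS (Protocol 9.5.1.5.7) | 6 and older | Fixed: "subjects aged 6 years and older at the time of consent/assent" | Not needed |
| LGPT (SAPs 5.6.6) | 10 pegs under 8, 25 pegs from 8 | Not stated | Yes, summarised separately under 8 and from 8 |
| CBCL (SAPs 5.6.6) | Forms 1.5-5 and 6-18 | Not stated | Yes, separate scores and summaries |
| EQ-5D-Y (Protocol 9.5.1.6) | Proxy 4 to 7, self 8 to 11 | Not stated | No |

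EQ-5D-Y therefore has neither an age anchor nor separate reporting.

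**Step 2: share of the 7 to <12 cohort that turns 8.** The documents give no age distribution. Assume that entry age is uniform within the cohort, which spans 5 years. A child turns 8 within t years if entry age lies in the t years below 8, so the share is t/5.

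- Week 23: t = 23 × 7/365.25 = 0.441 years; 0.441/5 = 8.8%, about 9%.
- Week 52: t = 52 × 7/365.25 = 0.997 years; 0.997/5 = 19.9%, about 20%.

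**Step 3: counts.** Take N = 160, the planned minimum (Protocol 9.3).

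- Ages uniform over 4 to <12: 160 × 0.441/8 = 8.8 children by Week 23, and 160 × 0.997/8 = 19.9 by Week 52.
- If 30% are aged 4 to <7 (the protocol's minimum): 160 × 0.70 × 0.441/5 = 9.9 and 160 × 0.70 × 0.997/5 = 22.3.
- If 50% are aged 4 to <7 (assumed): 160 × 0.50 × 0.441/5 = 7.1 and 160 × 0.50 × 0.997/5 = 15.9.

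That gives about 7 to 10 children by Week 23 and 16 to 22 by Week 52, before dropout.

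**Step 4: the mental-disability exemption.** Children with mental disabilities stay on proxy at every age and cannot switch. Their proportion is not given. If it is 25% to 50% (assumed), multiply by 0.75 to 0.50:

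- Cohort share: 4.4% to 6.6% by Week 23; 10.0% to 14.9% by Week 52.
- Children, over the range in Step 3: about 4 to 7 by Week 23; 8 to 17 by Week 52.

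**Step 5: effect on the cohort mean, for illustration only.** If switching children carry an average rater gap of d VAS points, the cohort's mean change moves by share × d. Nothing in the documents gives d. With d = 5 to 10:

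- No exemption: 0.088 × 5 to 10 = 0.4 to 0.9 points at Week 23; 0.199 × 5 to 10 = 1 to 2 points at Week 52.
- With 25% to 50% exempt: about 0.2 to 0.7 and 0.5 to 1.5 points.

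If parents rate higher in some families and lower in others, the average d and the shift are smaller. Individual change scores would still mix raters.

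**The case against.** A reader might infer that the plan makes every child change respondent at the eighth birthday. The documents do not say so, and nowhere say that age is re-read at each visit. The bands 4 to 7 and 8 to 11 together cover exactly the entry range, which is defined at consent. If age were re-read, a child without mental disabilities who turned 12 before Week 52 would fit neither band; reading age at entry leaves no such hole. The C-SSRS wording points the other way, because there the protocol fixes age in so many words. The text is ambiguous, and the supportable statement is that a switch can occur.

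A reader might also take the point shifts in Step 5 as an estimate of bias. They are not. The documents give no rater gap, no direction for it, no VAS variability and no meaningful difference to judge it against.

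Three further limits stand. In section 5.4.3 the change score is for the VAS only; the item tables mix raters but do not subtract one from another. Children who do not switch have the same type of rater at both visits, so pooling does not bias their own change. Neither SAP specifies a utility index, which weakens any argument from economic modelling.

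Programming specifications and table shells are separate documents and might separate respondents. They cannot be seen, so this neither closes nor confirms the gap. What survives is that the respondent rule has no anchor and neither SAP protects the change score from a switch.

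**Conclusion.** The concern holds in conditional form. Applying the stated age bands and the stated change score as written allows a proxy baseline to be subtracted from a self-rated follow-up for a child without mental disabilities who is 7 at Visit 2 and turns 8 before the later assessment.

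Under uniform ages within the 7 to <12 cohort, the affected share is at most about 9% by Week 23 and 20% by Week 52. Dropout and the disability exemption lower both figures. A cohort weighted towards 7-year-olds would raise them. If sites fixed the version at entry, nobody switches. No numerical bias can be claimed.

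The matter is minor. The endpoint is exploratory and descriptive, with no test or success criterion attached. It would be wrong to infer that the trial's main conclusions are at risk: the primary safety endpoint and the Japan efficacy criterion do not use EQ-5D-Y.

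**What to change.** In both SAPs (5.4.3, and Extension SAP 5.7), compute EQ-5D-Y change from baseline only when respondent type (proxy or self) is the same as at baseline, and summarise proxy and self ratings separately.

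In Protocol 9.5.1.6, with the matching synopsis text, state that respondent type is set by age at Visit 2 (or at consent), is kept at every later visit, and is recorded each time. This also settles who answers for a child who turns 12.

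The cost is one protocol statement and one SAP rule. If the protocol statement is followed, no change scores are lost, but some 8-year-olds able to self-report stay on proxy. If only the SAP rule is adopted, those children self-report and their change scores are dropped: no more than the counts in Step 3 under its assumptions. If data collection is over, the SAP rule is enough, provided that respondent type was recorded or can be recovered from the form used.

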9.5.2 Schedule of Procedures/Assessments – Core Study

9.5.2.1 Schedule of Procedures/Assessments

[Table 4](#) presents the schedule of procedures/assessments for the Core Study.

Table 4 Schedule of Procedures/Assessments in Study E2007-G000-311: Core Study

Phase	Pre-Treatment	Treatment Phase									Early Discontinuation ^d	Unscheduled
	Screening/Baseline	Titration ^a				Maintenance ^b				Follow-up ^{b,c}		
Visit	1	2	3	4	5	6	7	8	9			
Week	From up to -4 weeks ±3 days to Week 0 (outside of Japan) -4 weeks ±3 days to Week 0 (Japan only) (revised per Amendment 02)	0	2	5	8	11	15	19	23	27		
Procedures/Assessments												
Demography	X											
Informed consent/assent	X											
Inclusion/exclusion criteria	X	X										
Medical history	X											
Epilepsy medical history	X											
Prior/concomitant medication(s)	X	X	X	X	X	X	X	X	X	X	X	X
Prior/concomitant AED(s)	X	X	X	X	X	X	X	X	X	X	X	X
Neurological examination ^e	X								X	X	X	
Physical examination ^e	X								X	X	X	
Vitals ^f and weight ^g	X	X	X	X	X	X	X	X	X	X	X	X
Height ^g		X							X		X	
Adverse events	X	X	X	X	X	X	X	X	X	X	X	X
Study drug compliance			X	X	X	X	X	X	X		X	X
Dispense study drug		X	X	X	X	X	X	X	X ^h			X ⁱ
Retrieve unused study drug			X	X	X	X	X	X	X		X	X ⁱ
Dispense subject's diary	X	X	X	X	X	X	X	X	X ^h			X
Retrieve and review diary		X	X	X	X	X	X	X	X	X	X	X
Clinical laboratory tests ^j	X ^k					X			X ^k	X	X	X

Table 4 Schedule of Procedures/Assessments in Study E2007-G000-311: Core Study

Phase	Pre-Treatment	Treatment Phase									Early Discontinuation ^d	Unscheduled
		Screening/Baseline	Titration ^a				Maintenance ^b			Follow-up ^{b,c}		
Visit	1	2	3	4	5	6	7	8	9			
Week	From up to -4 weeks ±3 days to Week 0 (outside of Japan) -4 weeks ±3 days to Week 0 (Japan only) (revised per Amendment 02)	0	2	5	8	11	15	19	23	27		
Procedures/Assessments												
Thyroid (TSH, fT3, fT4) and IGF-1 testing	X								X		X	
Serum β-hCG (or hCG) test ^l	X											
Urine pregnancy test ^l		X	X	X	X	X	X	X	X	X	X	X
C-SSRS ^m	X	X	X	X	X	X	X	X	X	X	X	X
12-lead ECG ⁿ	X								X	X	X	X ^o
EEG ^p	X								X		X	X ^o
Perampanel PK sampling (plasma) ^{q,r}							X	X	X		X	X
Telephone call ^s		X	X	X	X	X	X	X				
ABNAS ^t	X ^u	X					X		X		X ^v	
Lafayette Grooved Pegboard Test	X ^u	X					X		X		X ^v	
Child Behavior Checklist		X							X		X	
EQ-5D-Y		X							X		X	
Clinical Global Impression		X							X		X	
Disposition		X							X		X	
IxRS	X	X	X	X	X	X	X	X	X	X	X	X

ABNAS = A-B neuropsychological assessment schedule, AE = adverse event, AED(s) = antiepileptic drug(s), β-hCG = beta-human chorionic gonadotropin (or hCG = human chorionic gonadotropin), C-SSRS = Columbia-Suicide Severity Rating Scale, eCRF = electronic case report form, EQ-5D-Y = EuroQol 5 Dimensions-Youth, fT3 = free triiodothyronine, fT4 = free thyroxine, IGF-1 = insulin-like growth factor-1, IxRS = interactive and response system, PK = pharmacokinetics, TSH = thyroid-stimulating hormone.

Table 4 Schedule of Procedures/Assessments in Study E2007-G000-311: Core Study

Phase	Pre-Treatment	Treatment Phase									Early Discontinuation ^d	Unscheduled
	Screening/Baseline	Titration ^a				Maintenance ^b				Follow-up ^{b,c}		
Visit	1	2	3	4	5	6	7	8	9			
Week	From up to -4 weeks ±3 days to Week 0 (outside of Japan) -4 weeks ±3 days to Week 0 (Japan only) (revised per Amendment 02)	0	2	5	8	11	15	19	23	27		
Procedures/Assessments												

- a: All visits to be done within ±3 days of the schedule. Each study visit is based on the actual prior visit (eg, Visit 3 is completed 2 weeks ±3 days of Visit 2, Visit 4 is completed 3 weeks ±3 days of Visit 3, Visit 5 is completed 3 weeks ±3 days of Visit 4). (revised per Amendment 02)
- b: Visit to be done within ±7 days of the schedule. Each study visit is based on the actual prior visit (eg, Visit 6 is completed 3 weeks ±7 days of Visit 5, Visit 7 is completed 4 weeks ±7 days of Visit 6, Visit 8 is completed 4 weeks ±7 days of Visit 7, Visit 9 is completed 4 weeks ±7 days of Visit 8). (revised per Amendments 02 and 03)
- c: The Follow-up Visit only applies to those subjects who complete the Core Study (or who discontinue the study early), but do not roll-over into Extension A and is to occur 4 weeks (±7 days) after Visit 9 or last dose of study drug.
- d: These assessments will be conducted for subjects who discontinue the study early for any reason after Visit 2.
- e: Physical and neurological examinations will only be performed at Visit 1 and Visit 9 and at the Follow-up Visit, and at the Early Discontinuation Visit (if applicable). For all other clinic visits during the study, the physical and the neurological exams will only be performed when there is a complaint from the subject. Clinically significant abnormal findings from the physical or the neurological examinations will be reported as AEs.
- f: Blood pressure and pulse will be taken.
- g: Weight and Height (without shoes) will be measured. Three measurements should be taken at each visit. Each measurement should be recorded as a separate entry on the Vital Sign eCRF.
- h: Only for those subjects who continue into Extension A.
- i: Unused study drug to be retrieved and study drug dispensed only for subjects requiring dose increases at Unscheduled Visits.
- j: Clinical laboratory tests include hematology, blood chemistry including lipid panel, and urinalysis.
- k: Fasting lipid and glucose samples to be taken at baseline and at end of treatment or early discontinuation, with fasting window (interval) between 2 and 4 hours.
- l: Female subjects age 8 years old and above, or of childbearing potential, only. If urine can not be obtained for pregnancy testing after screening, a serum pregnancy test will be performed. (revised per Amendment 01)
- m: Only for subjects aged 6 years and older at the time of consent/assent.
- n: If subject has a normal ECG baseline reading, but during any visit thereafter, the QT is measured as greater than 450 ms, 3 consecutive ECGs separated by 5 to 10 minutes will be performed to confirm the abnormality.
- o: During Unscheduled Visits, ECG or EEG will only be done if the results from the previous visit were deemed clinically significant by the investigator.
- p: EEG will be performed at awake and sleep state for all subjects.
- q: One blood sample (approximately 1 mL) for determination of perampanel plasma concentrations will be collected at any time during each of the specified visits.

Table 4 Schedule of Procedures/Assessments in Study E2007-G000-311: Core Study

Phase	Pre-Treatment	Treatment Phase									Early Discontinuation ^d	Unscheduled
	Screening/Baseline	Titration ^a				Maintenance ^b				Follow-up ^{b,c}		
Visit	1	2	3	4	5	6	7	8	9			
Week	From up to -4 weeks ±3 days to Week 0 (outside of Japan) -4 weeks ±3 days to Week 0 (Japan only) (revised per Amendment 02)	0	2	5	8	11	15	19	23	27		
Procedures/Assessments												

- r: Additional blood (approximately 1 mL/sample) will be drawn at the 1st report (where possible) of a serious adverse event or severe unexpected AE and at its resolution. (revised per Amendment 01)
- s: Telephone interviews with the subjects and/or caregiver will be conducted 1 week after Visit 2, Visit 3, Visit 4, Visit 5, Visit 6; and at the midpoint (±3 days) between each visit from Visit 7, Visit 8 and Visit 9 to ensure that subjects are completing their seizure diaries regularly and to assess AEs, study drug compliance, and concomitant medications, including AEDs. Subjects whose dose was decreased before the scheduled telephone interview will be strongly encouraged to return to the clinic (instead of the scheduled telephone interview) for further consultation with regard to study drug administration. The site will contact IxRS to receive further dispensing instructions. Subjects will then return for their regularly scheduled visit.
- t: ABNAS to assess patient-perceived cognitive effects of AED treatment, measuring 5 aspects of cognitive function: fatigue, memory, concentration, motor speed, and reading, using a 4-point scale.
- u: To be administered twice at Visit 1 (for training purposes only).
- v: Subjects who discontinue after Week 12 must have assessments performed at the Early Discontinuation Visit.

[Table 5](#) and [Table 6](#) present the Schedule of Procedures/Assessments for Extension A and Extension B of the study, respectively. (revised per Amendment 03)

